Eligibility Criteria: patient request for a labor epidural, BMI ≥ 35 . Eligibility criteria for anesthesia providers include those providers trained in both epidural placement and use of ultrasound for epidural placement.

Exclusion Criteria: BMI < 35 , patient refusal of a labor epidural, coagulopathy, platelets $< 80,000$, prior spine procedure or instrumentation, a diagnosis of scoliosis, and an intracranial or spinal mass. Exclusion criteria for anesthesia providers: those not trained in epidural placement or use of ultrasound for epidural placement.

- d. If participants will comprise more than one group or stratification, describe each group (e.g., treatment/intervention, placebo, controls, sham treatment) **and** provide the number of participants anticipated in each group.

Patient Participants: There will be a total of 150 participants randomized into two groups: palpation group (P) and ultrasound group (U). The randomization will be a 1:1 randomization. The technique will be chosen by randomly drawing a sealed envelope from a box that will contain a card with either palpation or ultrasound written on it. The palpation group will have an epidural placed after manual palpation of the spine. The ultrasound group will have an epidural placed after identifying midline with the ultrasound. There are no placebo or sham treatment groups. There will be no randomization of anesthesia provider. Any available anesthesia provider (if eligible to participate in the study) will place the epidural.

Provider Participants: Since we will continue with our standard practice of epidural placement, all providers trained in both ultrasound use and epidural placement will be able to place the epidural. This process will not be randomized. Providers will be chosen based on availability (i.e. if a patient requests an epidural at the time only one qualified provider is available, then that provider will place the epidural) or patient request (i.e. if a patient requests a certain qualified provider by name or level of training such as a fellow or faculty request). The provider training level will be documented on the data sheet.

e. Indicate which, if any, of the special populations listed below will be involved in the protocol. Include the Special Populations Review Form (SPRF) if indicated.

Pregnant Women: Attach SPRF—Pregnant Women, Fetuses, Neonates/Nonviable Neonates

Fetuses: Attach SPRF—Pregnant Women, Fetuses, Neonates/Nonviable Neonates

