Neonates/Nonviable Neonates: SPRF—Pregnant Women, Fetuses, Neonates/Nonviable Neonates

Prisoners: Attach SPRF—Prisoners

Minors (<19 years old): Attach SPRF—Minors

Employees or students at institution where research conducted

Persons who are temporarily decisionally impaired

Persons who are permanently decisionally impaired (e.g., mentally retarded)

Non-English Speakers

For each box checked, describe why the group is included **and** the additional protections provided to protect the rights and welfare of these participants who are vulnerable to coercion: Our goal is to demonstrate the usefulness of ultrasound in the placement of labor epidurals in severely obese parturients. This will be the patient population from which we will recruit. Informed, written consent will be obtained prior to persistent labor pains are experienced by the patient or medications are given to alter mental status. No treatment will be withheld from the patient. If she declines to participate in the study but requests an epidural, then an epidural will still be placed and anatomy will be identified by either palpation or ultrasound by the anesthesia provider, as both are considered standard practice.

If employees and students meet the inclusion criteria, they are eligible to participate. This special group, although included, will not be targeted by the protocol.

f. List any persons other than those directly involved in the study who will be at risk. If none, enter "None": None

g. Describe the process (e.g., recruitment, chart review) that will be used to seek potential participants (e.g., individuals, records, specimens). Research recruitment by non-treating physicians/staff may require completion of Partial Waiver of Authorization for Recruitment/Screening. (See <http://main.uab.edu/show.asp?durki=61981>.)

We will first identify the patients who are admitted to the labor & delivery unit for planned vaginal delivery. Those patients who have BMI ≥ 35 and desire a labor epidural will then be approached by either the PI or one of the co-investigators and consented for the study if they choose to participate. The recruitment process will begin prior to any obstetric intervention that may induce pain or altered mental status to the patient.

- h. If you will use recruitment materials (e.g., advertisements, flyers, letters) to reach potential participants, attach a copy of each item. If not, identify the source (e.g., databases) from which you will recruit participants.

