The IMPACT Labor & Delivery Room list will be used to identify potential participants.

- i. Describe the procedures for screening potential participants.

Once a patient is admitted to the labor and delivery suite, we will review their medical record to see if she is eligible to participate by meeting the above inclusion/exclusion criteria. Once this is determined, we will then discuss the study with the patient and obtain informed, written consent if they choose to participate.

16. Protocol Procedures, Methods, and Duration of the Study—in nontechnical language

- a. Describe the study methodology that will affect the participants—particularly in regard to any inconvenience, danger, or discomfort.

Providers: All investigators involved in this study have received training in use of the ultrasound for epidural placement and use the ultrasound in routine practice. Prior to being allowed to participate in the study, the anesthesia provider must demonstrate proficiency in the use of ultrasound. This will be accomplished on our obstetric anesthesia simulation model. Patients: Once informed consent is obtained, participants in the study will be randomized to either have the midline of their back located by ultrasound (U) or by palpation (P). After midline is located, the epidural catheter will be placed in routine fashion. Providers: Each provider will be timed on two events during epidural placement: (1) from start to completion of ultrasound exam/palpation exam and (2) from local injection of lidocaine at the skin to injection of the test dose. The primary outcomes for the study will be time required to perform the ultrasound/palpation exam of midline and time required for epidural placement. The secondary outcomes for the study will be (1) number of attempts or passes (defined as the need to remove the needle to the skin and redirect towards the epidural space) required for placement, (2) epidural failure rate (defined as inability to achieve a T10 level after 1 hour of epidural infusion and at least 10 mL of a local anesthetic bolus), and (3) time difference in provider level (junior resident, senior resident, attending).

- b. What is the probable length of time required for the entire study (i.e., recruitment through data analysis to study closure)?

1 year

- c. What is the total amount of time each participant will be involved?

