17. Describe the potential benefits of the research.

Patient/Provider: If identification of midline with an ultrasound decreases the time and number of attempts in placing a labor epidural, future use of the ultrasound will decrease patient discomfort and increase patient satisfaction. Use of the ultrasound would also decrease the amount of time that patient is positioned for epidural placement therefore decreasing the time that fetal monitoring is difficult.

18. Risks

- a. List the known risks—physical, psychological, social, economic, and/or legal—that participants may encounter as a result of procedures required in this protocol. Do not list risks resulting from standard-of-care procedures. *Note. Risks included in this protocol document should be included in the written consent document.*
Patients: Risks of the study include the potential to have more attempts to locate the epidural space with the epidural needle and a higher risk for failure of the epidural requiring replacement of the epidural catheter if requested. Although not proven, we believe these risks might be higher in the palpation group.

Patients and Providers: There is also the risk of breach of confidentiality.

- b. Estimate the frequency, severity, and reversibility of each risk listed.

N/A

- c. Is this a therapeutic study or intervention? Yes No
If Yes, complete the following items:
i. Describe the standard of care in the setting where the research will be conducted: _____
ii. Describe any other alternative treatments or interventions: _____
iii. Describe any withholding of, delay in, or washout period for standard of care or alternative treatment that participants may be currently using: _____
- d. Do you foresee that participants might need additional medical or psychological resources as a result of the research procedures/interventions? Yes No
If Yes, describe the provisions that have been made to make these resources available.

- e. Do the benefits or knowledge to be gained outweigh the risks to participants? Yes No
If No, provide justification for performing the research: _____

19. Precautions/Minimization of Risks

- a. Describe precautions that will be taken to avoid risks and the means for monitoring to detect risks.

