The anesthesia provider will be readily available to assess the patient during her labor and delivery per our standard practice. As per our standard practice, the anesthesia provider will evaluate the patient within 24 hours after delivery to assess for any complications.

Providers: If at any time the anesthesia provider feels uncomfortable or incapable of using the randomized technique to identify midline, he or she will be removed from the study. They will be allowed to freely choose their technique of choice in identifying midline. If this occurs, the participating patient in the study will be informed that she is no longer randomized and will be removed from the study. The patient will still receive standard of care treatment as described above.

At the mid-point of the study, our results will be reviewed by our statistician and if there is a highly significant result in either group, the study will be discontinued due to the overwhelming benefit of either palpation or ultrasound. Since patients are only recruited for the study the day of their epidural, no patients will need to be contacted if the study is discontinued.

- c. If hazards occur that might make the risks of participation outweigh the benefits for all participants, describe (i) the criteria that will be used to stop or end the entire study and (ii) any special procedures, precautions, or follow-up that will be used to ensure the safety of currently enrolled participants.

After a significant number of patients have been enrolled, we will perform a preliminary analysis of the data. If the data suggests there is a strongly significant benefit (or harm) to a certain group, such as much prolonged time in placement or a significantly improved success rate, we will end the study. Since patients are only enrolled in the study during their labor and delivery (as opposed to prolonged follow-up), there should be no special precautions that would need to be taken. Recruitment would just end due to the study ending.

20. Informed Consent

The answers below pertain to the patient participants. We are asking for a waiver of informed consent for the provider participants.

- a. Do you plan to obtain informed consent for this protocol? Yes No
If Yes, complete the items below.

If No, complete and include the Waiver of Informed Consent or Waiver of Authorization and Informed Consent, as applicable.

- b. Do you plan to document informed consent for this protocol? Yes No
If Yes, complete the items below.

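### Drawing a sealed envelope at random from a box fixes no allocation order, and no record of the draw is described, so a returned card and re-draw would not show in the data

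*Combined protocol and SAP*

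**What the plan says.** Item 15.d plans 150 patients in two arms and states that "The randomization will be a 1:1 randomization". The mechanism is given in one sentence: "The technique will be chosen by randomly drawing a sealed envelope from a box that will contain a card" naming one of the two techniques. The protocol does not mention numbering or opacity of the envelopes, a pre-generated list, a custodian, the number of cards in the box, the person who draws, or a log linking envelope to patient. The data sheet is said to hold the provider's training level (15.d) and any use of a second provider (19.a), and item 22.a adds the procedure times. Its full contents are not shown.

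Four other statements bear on the point:

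- **Consent comes first.** Item 16.a: "Once informed consent is obtained, participants in the study will be randomized". Under item 15.g, patients are "approached by either the PI or one of the co-investigators and consented for the study if they choose to participate".
- **No blinding is described.** Item 15.d: "There are no placebo or sham treatment groups". The provider carries out the allocated technique, and the primary outcomes are two procedure times.
- **The investigators hold a prior view.** Item 18.a, on extra attempts and epidural failure: "Although not proven, we believe these risks might be higher in the palpation group".
- **A patient can leave after allocation.** Item 19.b says that if a provider "feels uncomfortable or incapable of using the randomized technique to identify midline, he or she will be removed from the study", the provider may then choose the technique, and the patient also leaves the study.

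**The concern.** Concealed allocation has two jobs. Nobody should know the next assignment when a patient is enrolled, and nobody should be able to alter an assignment unseen once it is revealed. The box draw does the first reasonably well. It gives little protection on the second. With no fixed order there is no designated next envelope, so no gap in a sequence can reveal that one was passed over. With no recorded draw, a first card that was put back leaves nothing to compare the final assignment with.

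This matters more than usual here. Under item 14, providers are ordinarily free to choose either technique, so overriding a card would match local habit. The outcomes are open-label times and pass counts that depend on the operator and on how hard the patient is. If hard patients are moved between arms after opening, the arms differ before any effect of technique, and no analysis can undo that when the first draw is unrecorded. The removal rule in 19.b adds a second, visible route: patients can drop out for a reason tied to the allocated technique.

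**Working it through.** The plan has no figure to reproduce: it gives no alpha, power, effect size or SD behind the 150 patients. The check is therefore a reading of the mechanism, followed by an illustration of scale.

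**1. What the mechanism could reveal afterwards**

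- *Card returned and another drawn.* The number of envelopes used is unchanged. No order is broken and no described record shows the first card.
- *Envelope discarded.* This can be found by counting, but only if the number stocked is known and reconciled. The protocol states neither.
- *Selective enrolment on foreknowledge.* Limited, because the envelope is sealed, the draw is random and consent has already been given.
- *Removal under 19.b.* The removal is open, but without a log of opened envelopes such cases cannot be reliably counted by arm or told apart from re-draws.

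**2. Illustration of size (true effect zero)**

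From the documents: 150 patients at 1:1, so 75 per arm. Assumed: 30% of patients are hard, they are slower by 1 SD of the outcome, and the test is two-sided at 5%. Each arm then starts with 0.30 × 75 = 22.5 hard patients. Let s hard patients be switched from one arm to the other.

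- Bias (in SD) = (22.5 + s)/(75 + s) − (22.5 − s)/(75 − s)
- SE = √[1/(75 + s) + 1/(75 − s)], which is 0.163 when s = 0
- False-positive rate = P(Z > 1.96 − bias/SE) + P(Z < −1.96 − bias/SE)

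A single re-draw from a box that is about half and half changes the arm only about half the time. Re-drawing a quarter of one arm's hard patients therefore switches about 22.5 × 0.25 × 0.5 = 2.8.

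| Scenario | s | Bias (SD) | SE | False-positive rate |
|---|---|---|---|---|
| A quarter re-drawn once | 2.8 | 25.3/77.8 − 19.7/72.2 = 0.053 | 0.163 | 0.051 + 0.011 = 0.062 |
| A quarter end up switched | 5.6 | 28.1/80.6 − 16.9/69.4 = 0.106 | 0.164 | 0.094 + 0.005 = 0.099 |
| Half end up switched | 11.25 | 33.75/86.25 − 11.25/63.75 = 0.215 | 0.165 | 0.255 + 0.001 ≈ 0.255 |

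With one re-draw each, the last row means that essentially every hard patient first drawn to that arm was re-drawn.

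**3. Cross-check by simulation**

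Each setting had 4,000 runs with a box of 75 + 75 cards. For a share f of patients of above-median perceived difficulty, a palpation card was returned and re-drawn once. Perceived difficulty had correlation r with the outcome. Both f and r are assumptions.

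| f | Mean switched | Type I error, r = 0.3 | Type I error, r = 0.5 |
|---|---|---|---|
| 0 | 0 | 0.049 | 0.051 |
| 0.1 | about 2 | 0.053 | 0.051 |
| 0.25 | about 4.5 | 0.053 | 0.063 |
| 0.5 | about 9 | 0.060 | 0.097 |
| 1 | about 17 | 0.096 | 0.204 |

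Every run ended exactly 75/75 because returned cards stay in the box. If the box is stocked that way, the arm totals would not reveal re-draws.

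For comparison, 75 per arm detects (1.96 + 0.84) × √(2/75) = 0.46 SD with 80% power. The biases above run from about a tenth to almost half of that.

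**The case against.** The strongest reply is that much of this is silence, not a stated defect. Item 15.d asks only for the groups and their numbers, and item 16 asks for nontechnical language. Numbering, opacity, custody and a log may exist without being described. That is fair, and the absence of a log should be read as not described. It does not dispose of the point, because the random draw from a box is stated, and numbers on envelopes drawn in random order would still fix no sequence.

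Three stronger readings are tempting, and the documents do not support them:

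- *The recruiters draw the envelopes and steer patients.* The protocol says who obtains consent. It does not say who draws.
- *The difficulty of the back is seen before the draw.* Screening is by medical record, and the back examination is itself the allocated step. BMI is known at screening, but no inspection of the back before the draw is described.
- *The investigators' belief shows which way results would be tilted.* Item 18.a is a risk disclosure about attempts and failure, marked as unproven. Direction is open in any case: moving hard patients to ultrasound would make ultrasound look slower.

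It would also be too much to say that no tampering could ever be found. A discarded envelope can show up in a count, and returning a card means closing a broken seal. Nor is the 19.b removal rule evidence of hidden re-draws: the removal is open, and it is a separate exclusion after randomization that the same log would help to track. Finally, occasional re-draws do little harm, as the low rows in both tables show.

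**Conclusion.** The point holds as a weakness of the stated method. Allocation as written cannot be audited for a card returned after opening, and the 19.b rule lets patients drop out after allocation for a reason linked to the arm. Nothing shows that steering has happened or would happen.

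The size depends wholly on how often it occurs and on how strongly perceived difficulty predicts the outcome. Under the assumptions above, the false-positive rate is about 5-6% for occasional re-draws, about 10% if a quarter of one arm's hard patients end up switched, and about 26% if half do. The top figure is an extreme. The reason to act is that the plan could not show afterwards which of these applied, and prevention is cheap only before enrolment. The change should be made, but the point does not by itself invalidate the design.

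**What to change.** **In 15.d**, replace the box draw with sequentially numbered, opaque, sealed envelopes, filled from a computer-generated 1:1 list in permuted blocks of varying size. Someone already on the team who neither recruits nor places epidurals should prepare them, for example the statistician mentioned in 19.b. State who opens the envelope. Before opening, that person writes the patient's study number, date and time on the next envelope in order. Keep a log that accounts for every number, including envelopes opened for patients who later leave the allocated technique.

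**In the analysis**, assign each patient to the arm of the first envelope opened.

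**In item 19**, reconcile the text with this. As written, 19.b removes patients from the study when the provider abandons the technique or the procedure is stopped. Amend it so that patients who leave the allocated technique stay in the analysis in their allocated arm, and make clear that those handed to a second provider under 19.a do too. Their clinical care is unchanged. Changing 15.d alone would leave analysis by first envelope in conflict with 19.b.

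**Cost:** a small amount of preparation and a few paragraphs of text. No extra patients are needed, and none of the protocol's figures change.

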Summarize in 2-3 paragraphs past experimental and/or clinical findings leading to the formulation of this study. Include any relevant past or current research by the Principal Investigator. For drug and device studies summarize the previous results (i.e., Phase I/II or III studies).

The use of ultrasound has expanded into many areas of medicine including the identification of bony landmarks to facilitate epidural placement in obstetric anesthesia. Using ultrasound for epidural placement has become popular over the last decade with several studies being published on the topic. The likely increase in popularity for ultrasound use in the obstetric population is the need to more reliably locate bony landmarks as the traditional palpation technique has been shown to be an inaccurate way to accomplish this. One study reports that only 55% of the documented interspinous spaces during neuraxial anesthesia were correctly identified by palpation.

There have been several articles reporting the use of ultrasound in neuraxial anesthesia but none identifying its utility in the obese population. In patients with BMI $<$ 35 or those who have easily palpable spines, there is no statistical difference in number of attempts or patient satisfaction. In other studies where there were no limitations on BMI, there was a significant difference in number of attempts, patient satisfaction, successfulness of the block, and occurrence of dural puncture with the use of ultrasound. One study reports that these results are even more significant in resident trainees. In this study, investigators evaluated the use of ultrasound scanning by first year residents and found that identification of midline and measurement of the depth of the epidural space significantly decreased the number of attempts required and decreased the epidural failure rate.

Given the fact that the long-taught palpation technique can be inaccurate and studies have validated the use of ultrasound for epidural placement, ultrasound technique is routinely taught by the obstetric anesthesiologists to the anesthesiology residents at UAB. Also, since both techniques are considered standard practice at UAB, anesthesia providers (residents, fellows, and faculty) are free to choose either technique to locate bony structures of the back prior to epidural placement. Since no current study has specifically addressed its use in the obese pregnant patient, we would like to validate its use in this population.

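### Provider training level is recorded but used neither in the allocation nor in any stated comparison of the arms, which risks lost precision and chance imbalance on both primary times

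*Combined protocol and SAP*

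**What the plan says.** Section 15.d sets a 1:1 allocation of 150 patients: "The technique will be chosen by randomly drawing a sealed envelope from a box that will contain a card with either palpation or ultrasound" on it. It describes no strata or blocks. On the operator it says: "There will be no randomization of anesthesia provider. Any available anesthesia provider (if eligible to participate in the study) will place the epidural". The same section explains that the operator depends on who is free or whom the patient asks for, and that a patient may ask for a level of training. It adds: "The provider training level will be documented on the data sheet".

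Section 16.a makes two operator times the primary outcomes: the duration of the midline exam, and the time from skin infiltration to the test dose. The third secondary outcome, in sections 13 and 16.a, is the difference in time between junior residents, senior residents and attendings. Section 15.c also admits obstetric anesthesiology fellows, who have no place in those three categories.

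Section 14, after describing studies in which ultrasound changed attempts, satisfaction, block success and dural puncture, says: "One study reports that these results are even more significant in resident trainees".

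Section 16.a places randomization after consent. No section says whether the operator is known when the envelope is opened. No section gives a method for comparing the arms, with or without provider level.

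**The concern.** Operator experience plausibly affects how long the exam and the placement take, and the protocol thinks it worth measuring. A single unstratified draw leaves the mix of junior and senior operators in each arm to chance. If one arm happens to have more juniors, part of the time difference between arms reflects who operated rather than which technique was used. If the arms are compared without level, the spread between levels also stays in the error term and widens the interval for the ultrasound effect. The by-level results may then rest on unequal arm sizes within a level.

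The order of events matters too. The operator is not randomized and may be settled after the technique is known, so the documents do not rule out the arm influencing who takes the case.

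**Working it through.** **1. The plan's own figure.** The only figure is the total of 150. It comes without alpha, power, effect size, SD or test, so it cannot be reproduced. I take 75 per arm from the 1:1 ratio; the split of cards in the box is not stated. Junior share, time gaps, alpha and power below are assumptions.

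**2. Chance imbalance in operators.** Let K = 150p be the junior-operated cases and k the number falling in one arm. Then k is hypergeometric (150, K, 75), and the between-arm difference in junior share is D = (2k - K)/75. Its SD is (2/75) x sqrt(75 x p(1-p) x 75/149). At p = 0.40: 75 x 0.24 = 18; 18 x 75/149 = 9.06; square root 3.01; times 2/75 gives 0.080. The 95% range is 1.96 x 0.080, or about ±16 points.

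| Junior share | SD of D (points) | P(10 points or more) | P(15 or more) | P(20 or more) |
|---|---|---|---|---|
| 20% | 6.6 | 15% | 2.4% | 0.2% |
| 33% | 7.7 | 23% | 5.6% | 0.9% |
| 40% | 8.0 | 24% | 6.6% | 1.2% |
| 50% | 8.2 | 19% | 5.0% | 2.2% |

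The probabilities do not rise smoothly with p because D moves in steps of 2/75 = 2.7 points.

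**3. Effect on the estimate.** Shift in the arm difference = D x the junior-senior gap in time. For assumed gaps of 2, 5 and 10 minutes, a 10-point imbalance shifts it by 0.2, 0.5 and 1.0 minutes. At the 95% limit of imbalance (13-16 points) the shift is about 0.3, 0.6-0.8 and 1.3-1.6 minutes. For scale, section 16.c expects placement to take 5 to 30 minutes. Section 16.e puts the exam under 5 minutes, so a 10-point imbalance could shift mean exam time by less than 0.5 minutes (0.10 x 5).

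**4. Precision.** With a junior-senior gap of g within-level SDs, v = p(1-p)g². The share of variance explained by level is v/(1+v), and comparing within level narrows the standard error by 1 - 1/sqrt(1+v). At p = 0.40:

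| g (SD) | v | Variance explained | Narrower SE |
|---|---|---|---|
| 0.25 | 0.015 | 1.5% | 0.7% |
| 0.5 | 0.06 | 5.7% | 2.9% |
| 1.0 | 0.24 | 19% | 10% |
| 1.7 | 0.69 | 41% | 23% |

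**5. Power, for scale.** With two-sided alpha 0.05 and 75 per arm, 80% power corresponds to an effect of (1.960 + 0.842) x sqrt(2/75) = 0.457 within-level SD. At that effect, and for junior shares of 20-50%, an analysis ignoring level has 79-80% power at g = 0.25, about 78% at g = 0.5, and 71-74% at g = 1.0.

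**6. Type I error.** In simulations of the unadjusted two-sample comparison (15,000 runs per setting), overall type I error was 4.9-5.2%. Restricted to trials with an imbalance of 15 points or more, it was about 8% at g = 0.5 and 13-14% at g = 1.0.

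**7. Analysis or envelopes?** Under the existing unstratified draw, adjusting for level leaves a standard error above that of perfect balance by roughly (levels - 1)/(2 x 149): 1/298 = 0.3% for two levels and 2/298 = 0.7% for three. Simulation gives the same figures. Nearly all the precision gain therefore comes from the analysis.

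**The case against.** Randomization already deals with chance imbalance: the comparison is unbiased on average, and step 6 shows the overall error rate holding near 5%. Large imbalances are uncommon and, for modest gaps between levels, move the estimate by well under a minute. Level is recorded, so one sentence in an analysis plan would recover the precision without changing the envelopes. Stratified envelopes have costs of their own. Short fixed blocks in an unblinded single-unit trial can be guessed, and section 19.b lets a provider's discomfort with the assigned technique remove the patient from the study. Under section 19.a a second provider may take over a difficult placement, so the stratum may not describe whoever finishes.

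Most of this stands, and it determines the order of the fix: analysis first, stratified envelopes as a preference. It does not remove the point, because that analysis sentence is absent and the order of provider choice and envelope opening is not stated.

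A reader might go further in two ways. One is to infer that the protocol regards training level as a main driver of time and attempts. It does not say so: level appears as a secondary outcome for time only, and the trainee finding in section 14 is about how much ultrasound helps, described through attempts and failure rather than time. The other is to infer that operators will differ systematically between arms. The documents leave this open, since the operator may be chosen after allocation, but nothing in them shows that it will happen.

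**Conclusion.** The point holds as a matter of precision, chance imbalance and an unguarded sequence of events. It is not a demonstrated bias. A factor that the protocol records, expects to relate to time and has reason to think may modify the ultrasound effect enters neither the allocation nor any stated arm comparison.

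The size depends on inputs the documents do not give. For junior shares of 20-50%, a noticeable imbalance (10 points or more) would arise in roughly one trial in four to seven. The precision gain is negligible if levels differ by up to half an SD and worthwhile at about 1 SD or more. The change is justified mainly because it is almost free and affects both primary outcomes.

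**What to change.** 1. State that each primary time is compared between arms with provider level as a stratum or covariate, using the level of the provider who starts the procedure. Define the levels as junior resident, senior resident and fellow/attending, so that fellows are placed.
2. State in sections 15.d and 16.a that the provider and level are recorded before the envelope is opened, so that the arm cannot influence who operates.
3. Preferably, replace the single box with a separate 1:1 envelope set for each level, using varied or larger blocks so that the next allocation cannot be guessed. This also keeps the arms close to equal within each level for the third secondary outcome.

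Cost: a few sentences and, for item 3, up to three envelope sets instead of one. Randomization must wait until the provider is known, so the timing in section 16.a needs rewording. Level is already on the data sheet, and no extra patients or staff are needed.
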